The primary objective of this study is to examine in a double blinded and randomized trial the efficacy of Recombinant Human lactoferrin (rhLF) in reducing chronic inflammation as measured by IL-6 and sTNFR1 in the bloodstream. Secondary objectives include assessing the efficacy of rhlactoferrin (rhLF) in attenuating cognitive decline as measured by the Digit Symbol Substitution Test and Trail Making Test, as well as improving physical mobility as measured by performance on 4 meter and six-minute walk tests. The tertiary objective of this study is to gather information about the tolerability of and adherence to oral rhlactoferrin (rhLF) among older adults with CI over a three-month period.

3. Background

Chronic Inflammation and Biological Mediators:

Chronic inflammation (CI) as defined by chronic elevation in serum inflammatory measures is a known risk factor for a host of adverse health outcomes in older adults (3;17;18). The etiology of CI is complex with increased chronic disease burden, fat mass, free radicals, and senescent cells, dysfunctional mitochondria, altered microbiome, and decreased GI tract barrier function all potentially contributing (19-25). Dozens of population studies have detailed significant associations between pro-inflammatory measures and functional and mobility decline, frailty, worsening chronic illness, cognitive decline, mortality and reduced gait speed (1;2;26;27;28). Although these relationships were often considered to be epidemiological phenomena rather than causal, evidence suggests that chronic exposure to some inflammatory mediators can lead directly to molecular and tissue changes that contribute to the observed adverse outcomes (29;30-34). Specifically, evidence suggests that IL-6, sTNFR1 and other molecules directly and negatively impact skeletal muscle and neurologic tissue through impairment of satellite cells, through the triggering of cell death pathways, and through other mechanisms (35-44). Figure 1 provides a conceptual overview for a biologically plausible pathway between CI and health-related declines; lactoferrin is hypothesized to impact inflammatory mediators and their downstream effects.

Chronic Inflammation and Cognitive Decline:

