Baseline Visit (BV): Individuals meeting eligibility criteria (described below) will be scheduled for a baseline visit. This visit will consist of a brief medical history review and blood draw, along with outcome measurements described thoroughly below. At the end of the visit, the pharmacy or site coordinator will distribute the randomized study product with instructions. A structured walking program and encouragement of physical activity for participants in all treatment arms will be included. Participants will also receive an accelerometer for home mobility measurement along with detailed instructions for use.

Follow up visit (FUV): Monthly in person visits will take place, with telephone contact every two weeks by study staff between visits to help maintain adherence and assess for adverse effects. Pill counts and side effect assessments will take place at FU1, FU2, and FU3. FU6 will include measures checked in Table 2 and described below.

Table 2

	PSC	SV	ABT	BV	FU1	FU2	FU3			FU6.
Phone Screen	X									
Medical History		X								
Brief Medical History Review				X	X	X	X			X
Informed Consent		X								
Demographics		X								
Randomization				X						
Frailty Assessment				X			X			X
Activity Assessment				X			X			X
Vital Signs (BP, HR, Hgt,Wgt. Temp, Resp.)		X	X	X	X	X	X			X
Short Physical Performance Battery				X			X			X
Side Effect Assessment					X	X	X			
4 meter walk		X		X			X			X
Six-minute walk test				X			X			X
Blood Draw		X	X	X	X		X			X
Physical Exam		X								
MMSE		X								
Cognitive measures (Trail Making Test and Digit Symbol Substitution Test)				X			X			X
Accelerometry				X			X			X
Pill Calendar				Marked Daily to end of Month 3						
Abbreviations: PSC: Prescreening contact; SV: Screening visit; ABT Additional Blood test (to further determine eligibility for those whose cytokine levels are above threshold); BV: Baseline visit; FU1-6: Follow up months 1-6 of pilot study										

All laboratory results will be reviewed by study physicians during the study and there will be frequent review

of adverse and/or other unexpected events. Following study protocol, all adverse events will be reported to the IRB and National Institute on Aging (NIA) as per requirements. Participants will be able to report issues at study contacts but will also be provided with a number to call ad hoc as needed if issues related to study participation arise. If participants choose to withdraw from the study, their medical care will not be affected in any way.

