Side Effect Assessment: A Side Effect Assessment will be conducted at FU1, FU2, and FU3. The purpose of this assessment is to monitor participants' responses to lactoferrin and to assess for any adverse side effects.

Activity Assessment: Participants will answer questions about their physical activity and energy levels. This assessment is conducted at BV, FU3, and FU6.

Frailty Assessment: This assessment is completed at BV, FU3, and FU6. This assessment measures participants' walking speed and grip strength, and includes questions about weight loss.

Vital Signs: Participants' vital signs will be measured at every study visit. These measurements include height, weight, blood pressure, respiratory rate, and temperature.

Additional Physical and Functional Measurements:

Home Mobility Measurement: An Acti-Graph® Link Activity monitor will be placed on the participant's non-dominant wrist at the end of the BV. This model includes an ambient light designed to provide environmental information and a gyroscope and magnetometer to capture position and rotational data. Accelerometry counts will be measured at a sampling frequency of 80 hertz for 7 days immediately

after completing the BV, 3-month, and 6-month visits. Participants will be asked to wear the device at all times except when swimming for >30 minutes. Monitors will be mailed via pre-addressed express mail packets where all raw data will be downloaded using commercial software (ACTLIFE, v6) to derive activity data in g force and counts/min. The JHU Statistical Methods for Applications and Research in Technology ("SMART"-stats) group, developers of the "movelets" technology that enables the use of raw data (62), will use collected data to: (i) characterize cumulative daily activity, (ii) assess daily circadian patterns of activity, (iii) assess physical activity variability, (iv) model patterns of daily activity, and (iv) estimate walking speed (62, 63, 64). These measurements greatly extend what is normally available from accelerometers and will complement mobility measures by describing function enacted in daily life.

5. Inclusion/Exclusion Criteria

Inclusion: Age 70 and older; able to complete 4- meter timed walk; walking speed ≤ 1.0 m/sec; serum IL-6 level ≥ 2.5 pg/ml or TNFR1 level ≥ 1500 pg/ml. Consistent with NIH guidelines, both genders and minority persons are enrolled. Participants will be followed for 6 months to investigate the effects of the treatments on gait speed and other outcomes.

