Exclusion criteria: Participants with IL-6 levels above 30.0 pg /ul. Daily anti-inflammatory drug use (prednisone, Advil, Aleve, Remicade, Enbrel, methotrexate, standing NSAID, aspirin greater than 325 mg per day), lower extremity mobility disability caused by Parkinson's disease, CVA with residual motor deficit, severe osteo or rheumatoid arthritis, symptomatic claudication, hospitalization within 3 months for MI, angina, infection requiring antibiotics, or joint replacement, and for other reasons that markers may be elevated such as active or chronic malignancies MMSE < 21.

6. Drugs/ Substances/ Devices

Lactoferrin is a basic glycoprotein initially identified in milk but subsequently identified in most exocrine secretions and in granules secreted from neutrophils (8). It has pleiotropic anti-inflammatory effects that range from the coating and degradation of invading organisms and their antigenic cellular components, to the sequestration of free iron needed by invading organisms to thrive, to the suppression of inflammatory (NFkB) signaling, and the modulation of the adaptive immune system (8-10;12). A recent study that characterized a lactoferrin knock out mouse demonstrated a colonic inflammatory phenotype which suggests an important role for lactoferrin at the interface between the colon and the immune system (11). Given the evidence for altered immunogenic intestinal flora in frail older adults, and the decreasing barrier function of the aging intestinal epithelium, and the known anti-inflammatory functions of lactoferrin, the use of oral lactoferrin for CI suppression in older adults is highly biologically plausible. (13-15;65-68). Beyond this mechanistic rationale, oral lactoferrin has demonstrated to safely and significantly reduce the incidence of neonatal sepsis in prior studies (69) and post-antibiotic diarrhea in older nursing facility residents (70). In older adults, lactoferrin was well tolerated in late stage cancer patients and increased overall survival in a study that did not include inflammatory measures (71, 72). A prior study of bovine lactoferrin demonstrated significant reductions of CRP and IL-6 levels in post-menopausal women treated for 6 months with minimal or no side effects (16). Lactoferrin has previously been used as a chronic diarrhea intervention in other vulnerable populations with minimal safety concerns and few if any adverse outcomes related to lactoferrin (70;73,74).

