For this study, Recombinant Human lactoferrin (rhLF) a partially iron saturated form of lactoferrin in 250 mg capsules and matching placebo capsules will be provided by Ventria Bioscience Biotech company at bulk pricing. Each capsule will contain 250 mg of rhlactoferrin (rhLF) as active ingredient and cellulose, magnesium stearate, and silicon dioxide as inert ingredients. Subjects will receive either 1500 mg of rhlactoferrin in capsule form twice a day or a placebo in exact matching capsules. Dosing will be six 250 mg capsules twice a day based on prior dosing used safely in studies of diarrhea in a nursing home population (70). This treatment will take place for approximately 3 months (87 days). Recombinant human lactoferrin (rhLF) is produced through standard methods of genetic modification and plant transformation. The rice grain in which the protein accumulates is stable and well suited as a production system Recombinant human lactoferrin has been purified from transgenic rice using standard food industry procedures and current good manufacturing practices. Each placebo capsule will contain cellulose, magnesium stearate, and silicon dioxide, manufactured in full compliance with all pharmaceutical regulation.

7. Study Statistics

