Based on a two-sided two-sample t-test with a Type I error of 0.05, a sample size of 23 subjects per group (46 in total) will achieve 80% power to detect a difference of 0.86 SD or greater in logIL-6 between the treatment group and the placebo group at the end of the 6-month trial. Secondly, we will compare the linear rate of change in logIL-6 between the treatment and the placebo groups by modeling the individual trajectories of the outcome. With 20 subjects per group, three repeated measurements of IL-6 assessed at baseline, 3, and 6 months, and a correlation of 0.54 between measurements, we will have 80% power to detect a difference of 1.3 SD units (equivalent to a cross-sectional between-group difference of 0.65SD different at 6 months) or greater in the yearly rate of change in logIL-6 between the treatment and the placebo group. The within subject between-measurement correlation of 0.54 was estimated using longitudinal data from the Women's Health and Aging Study II. Therefore, using longitudinal data, we will have adequate power to detect a difference similar to the 0.63 SD (or 2.5 pg/mL) difference observed at the end of a 6-month, randomized clinical study of a ribonuclease-enriched lactoferrin supplement in post-menopausal women (16). Given these calculations, we are aiming to recruit up to 60 individuals, 30 in each group, in order to maximize our ability to detect differences between treatment and placebo groups. This increased number beyond what are calculated here will take into account anticipated drop outs during the treatment period and leave us with an estimated 'complete completer' group of 46 total. In addition, we are estimating that we will need to have at least 250 individuals recruited into the protocol in order to identify those eligible by inflammatory mediator criteria listed above.

8. Risks

Six Minute Walk Test: This is performed by having the participant walk along a straight hallway for six minutes and measuring the distance walked and the sensation of leg fatigue and dyspnea. The participant may stop at any time if they feel uncomfortable. As with any exercise test, there is a theoretical risk that a participant could suffer cardiac risk from arrhythmia or ischemia, or orthopedic risk from falling or stumbling. Risks are minimized by conducting the test in a medically supervised environment with trained personnel.

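### Study product stops at about month 3, but both logIL-6 analyses rest mainly on month 6 and neither tests the end-of-treatment difference

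*Combined protocol and SAP*

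**What the plan says.** **Treatment period.** Section 6 states: "This treatment will take place for approximately 3 months (87 days". Table 2 in Section 4 agrees: the pill calendar is "Marked Daily to end of Month 3".

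**Objective.** Section 2 sets the primary aim as efficacy "in reducing chronic inflammation as measured by IL-6 and sTNFR1 in the bloodstream", with no time point. Section 4 names serum IL-6 and sTNFR1 as the primary outcome, again without one.

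**Follow-up.** Section 5 says: "Participants will be followed for 6 months to investigate the effects of the treatments on gait speed and other outcomes".

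**Analyses.** Section 7 gives two for logIL-6. The first is a two-sample t-test "between the treatment group and the placebo group at the end of the 6-month trial", with 23 per group and 80% power for 0.86 SD. In the second, "we will compare the linear rate of change in logIL-6 between the treatment and the placebo groups", using values at baseline, 3 and 6 months, 20 per group and a correlation of 0.54. Its detectable effect, 1.3 SD per year, is restated as 0.65 SD at 6 months.

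**Benchmark.** Section 7 supports the second analysis with a 0.63 SD "difference observed at the end of a 6-month, randomized clinical study". Section 6 describes that study as showing "significant reductions of CRP and IL-6 levels in post-menopausal women treated for 6 months".

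**The concern.** Month 6 is the only time point attached to a primary-outcome comparison, and it falls about three months after product stops. As written, Section 7 asks whether IL-6 still differs three months off product, while Section 2 asks whether lactoferrin reduces it. These are different questions, and nothing in the documents says that the first was intended.

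The benchmark has the same problem. It is an end-of-treatment effect in women treated for 6 months, so it does not carry over to a value taken three months after stopping. The 0.86 SD is a detectable difference with no cited source.

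Section 1 says the pilot will be used to develop a more definitive trial. An agent that never worked and one whose effect wore off imply different next trials. A null result at month 6 does not separate them, and a month-3 comparison chosen after seeing that result would be post hoc.

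**Working it through.** **Inputs from Section 7:** 23 per group (t-test), 20 per group (slope), two-sided 0.05, correlation ρ = 0.54, visits at t = 0, 0.25 and 0.5 years, effects of 0.86 and 0.63 SD.

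**Assumptions:** unit SD at each visit, equal correlation between visits, complete data, and a share r of the month-3 effect remaining at month 6. The documents do not give r, so it runs from 1 to 0.

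**1. The plan's own figures.** For the t-test, the noncentrality is 0.86 × √(23/2) = 2.92 on 44 df, which gives 81.4% power. The stated 80% reproduces. The stated slope figure (80% for 1.3 SD per year with 20 per group) does not: the same inputs give about 57% with separate intercepts, or 70% with a common baseline mean. That is a separate matter, and nothing below relies on the stated slope power.

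**2. What the slope uses.** The weights are (t − 0.25)/Σ(t − 0.25)², with Σ = 0.0625 + 0 + 0.0625 = 0.125. They equal −2, 0, +2. With separate intercepts, the slope is therefore (month 6 − baseline)/0.5 year, and month 3 drops out. The SD of that change is √(2 × (1 − 0.54)) = 0.959. Section 7 does not write out the model. If the arms share a baseline mean, generalised least squares gives weights of −1.17, 0.33 and 1.83, so month 6 still dominates. In either form, a straight line cannot describe a fall on treatment followed by a return.

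**3. Power at 23 per group, 0.86 SD at month 3.**
- Month-6 t-test: noncentrality 0.86r × √(23/2).
- Separate-intercept slope: the same, divided by 0.959.
- Common-baseline slope: expected contrast 0.86 × (0.33 + 1.83r), standard error 0.490.

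At r = 0.5 the three noncentralities are 1.46, 1.52 and 1.074/0.490 = 2.19.

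| Share retained at month 6 | Month-6 t-test | Slope, separate intercepts | Slope, common baseline | Month-3 t-test |
|---|---|---|---|---|
| 100% | 81% | 84% | 96% | 81% |
| 75% | 57% | 61% | 83% | 81% |
| 50% | 30% | 32% | 57% | 81% |
| 25% | 11% | 12% | 27% | 81% |
| 0% | 5% | 5% | 9% | 81% |

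At the stated 20 per group, the half-retained slope has 28% (separate intercepts) or 51% (common baseline).

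**4. Month 3 with baseline adjustment.** A model with visit as a category and a common baseline mean has residual SD √(1 − 0.54²) = 0.842. That gives 92% at month 3 for 0.86 SD. The same adjusted contrast at month 6 with half retained has 40%.

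**5. At the benchmark 0.63 SD.**

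| Share retained at month 6 | Month-6 t-test | Slope, separate intercepts | Slope, common baseline |
|---|---|---|---|
| 100% | 55% | 59% | 78% |
| 50% | 18% | 19% | 35% |

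At month 3 the figures are 55% (t-test) and 70% (visit model).

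**The case against.** The strongest reply is that the harm is conditional. No rate of fading is given, and if the whole effect lasts to month 6 nothing is lost. That stands for the power figures, which are a range. It does not touch the mismatch between objective, treatment period and time point, and the plan gives no reason to expect the full persistence that its month-6 power would require.

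Six-month follow-up is plainly deliberate, so month 6 may be a chosen endpoint. That explains the visit, but not the lack of a month-3 cytokine contrast. If persistence is the question, the plan should say so.

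Section 7 is largely a sample-size justification, and month-3 IL-6 will be measured, so the difference can be estimated whatever is prespecified. That also stands: prespecification decides whether the month-3 answer is confirmatory, not whether one exists.

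Three cautions on the numbers are fair:
- The 81% at month 3 assumes the full 0.86 SD is reached by day 87, whereas the only cited effect followed 6 months of treatment. An effect that is larger at month 6 than at month 3 lies outside the range shown.
- At 0.63 SD the t-test has only 55% even with full retention, so part of that shortfall comes from effect size and not from timing.
- Baseline adjustment accounts for some of the visit model's advantage. The like-for-like comparisons, month 3 against month 6 with half retained, are 81% against 30% unadjusted and 92% against 40% adjusted.

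**Conclusion.** The concern holds. The primary comparison is placed about three months after product stops, the linear slope gives the end-of-treatment value little or no weight, and no month-3 contrast is planned or powered. With 0.86 SD at month 3 and 23 per group, power at half retention is 30% (t-test), 32% (separate-intercept slope) or 57% (common-baseline slope); at zero retention it is 5 to 9%. With full retention there is no loss. These figures rest on an assumed retained share, equal correlations of 0.54, complete data, and the full effect being present by month 3. The mismatch itself rests on none of them. Because it concerns the primary outcome, it should be settled before any unblinded analysis.

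**What to change.** Reconcile the objective, the treatment period and the primary time point. No view is taken on treatment length.

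- Since the stated objective is to reduce inflammation, prespecify the between-group difference in logIL-6 and sTNFR1 at FU3 as primary.
- Replace the linear slope with a repeated-measures model with visit as a category: BV, FU3, FU6, and FU1 if cytokines are assayed there. Report FU6 as a secondary measure of persistence.
- Say how the two markers share the type I error. If each were tested at 0.025, the FU3 t-test would have 72% for 0.86 SD and 43% for 0.63 SD.
- Restate power for FU3, and note that the 0.63 SD came from 6 months of treatment.
- If persistence is the intended primary question, state it and still prespecify the FU3 contrast.

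**Cost.** Section 7 is rewritten, with matching edits to Sections 2 and 4 if the time point is stated there. This is a protocol amendment, on which Section 8 has the DSMB make recommendations. IL-6 at baseline, 3 and 6 months is already planned, and blood is drawn at FU1, FU3 and FU6, so no visits or participants are added. The month-6 comparison becomes secondary under the first option. If the whole effect persisted, the common-baseline slope would have been slightly more powerful (96% against 92%).

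### The 80% power claimed for the longitudinal logIL-6 slope comparison does not follow from its stated inputs, which give about 57%; the claim of adequate power for a 0.63 SD effect therefore fails.

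*Combined protocol and SAP*

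**What the plan says.** Section 7 of the combined protocol and SAP contains two power calculations for logIL-6.

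- **Cross-sectional, at 6 months.** "Based on a two-sided two-sample t-test with a Type I error of 0.05", 23 per group give 80% power for 0.86 SD.
- **Longitudinal.** The plan says "we will compare the linear rate of change in logIL-6 between the treatment and the placebo groups by modeling the individual trajectories of the outcome". The inputs are: "With 20 subjects per group, three repeated measurements of IL-6 assessed at baseline, 3, and 6 months, and a correlation of 0.54 between measurements". The stated result is that "we will have 80% power to detect a difference of 1.3 SD units" in the yearly rate of change, described as "equivalent to a cross-sectional between-group difference of 0.65SD different at 6 months".

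From the second calculation the plan concludes that "we will have adequate power to detect a difference similar to the 0.63 SD" found in a 6-month trial of a lactoferrin supplement in post-menopausal women. It then sets enrolment at up to 60 (30 per group) to allow for dropout, and expects 46 completers, which is 23 per group if evenly split.

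**The concern.** The two calculations do not fit together. The t-test needs 23 per group to detect 0.86 SD, yet the slope analysis is said to detect 0.65 SD with only 20 per group. A gain of that size would need repeated measurements that remove most of the variance. With three equally spaced visits and a correlation of 0.54, they remove very little.

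The slope calculation is the plan's only support for saying that the trial can detect an effect of the size seen before, because the t-test is claimed only for 0.86 SD. IL-6 is one of the two primary outcome markers (Sections 2 and 4), and Section 1 says that the results will be used to develop a more definitive trial. If the real chance of missing a 0.63 SD effect is about 40–45% and not about 20%, a null result could be read as stronger evidence against lactoferrin than it is.

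**Working it through.** **Inputs, all from Section 7:** n = 20 per group; visits at t = 0, 0.25 and 0.5 years; correlation ρ = 0.54; stated difference 1.3 SD/year; target effect 0.63 SD at 6 months, which is 0.63/0.5 = 1.26 SD/year. The two-sided 0.05 level is stated for the t-test and assumed here for the slope test. Equal correlation between all pairs of visits and separate group intercepts are also assumed, since the plan gives no other structure.

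**The plan's first figure.** For 23 per group and 0.86 SD, the noncentral t gives 81.4% power. That agrees with the stated 80%.

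**The plan's second figure.** The conversion 1.3 × 0.5 = 0.65 SD at 6 months is right. The power is not:

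1. Sum of squared time deviations: Sxx = 0.25² + 0 + 0.25² = 0.125.
2. Variance of one person's slope: (1 − ρ)/Sxx = 0.46/0.125 = 3.68 SD² per year².
3. SE of the group difference: √(2 × 3.68/20) = 0.607 SD/year.
4. Power at 1.3: Φ(1.3/0.607 − 1.96) = 57.3% (noncentral t: 55.1%).
5. Difference detectable with 80% power: (1.96 + 0.8416) × 0.607 = 1.70 SD/year, or 0.85 SD at 6 months.
6. Number needed for 1.3 SD/year: 2 × 3.68 × 2.8016²/1.3² = 34.2, so 35 per group. For 1.26 SD/year it is 37 per group.

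**Check without the slope formula.** With three equally spaced visits, the fitted slope is the 6-month value minus the baseline value, divided by 0.5; the middle visit drops out. The change score has variance 2(1 − 0.54) = 0.92 SD², against 1.0 SD² for the 6-month value alone. The t-test with 20 per group detects about 0.91 SD, so an 8% smaller variance cannot bring that down to 0.65 SD.

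**By number analysed** (normal approximation; noncentral t in brackets):

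| Per group | Detectable, SD/year | Power at 1.3 SD/year | Power at 0.63 SD (1.26 SD/year) |
|---|---|---|---|
| 20 | 1.70 | 57% (55%) | 55% |
| 23 | 1.59 | 63% (61%) | 61% |
| 30 | 1.39 | 75% (73%) | 72% |

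**Other readings, at 20 per group and 1.3 SD/year:**

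| Reading | Power |
|---|---|
| Autoregressive correlation, 0.54 per 3 months | 41% |
| Adding the month-1 draw | 64% |
| Baseline-adjusted 6-month value | 69% |
| One-sided 0.05 slope test | 69% |
| Common-baseline slope model | 70% |
| Common baseline plus the month-1 draw | 72% |
| Common-baseline slope model, one-sided 0.05 | 80% (79.6%) |

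With the stated slope model and 20 per group, 80% power needs a correlation of about 0.73.

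**A possible source, which the documents do not confirm.** If the time variance is computed with divisor 2 (three visits minus one) and then multiplied by 3, Sxx becomes 0.1875. With 23 per group, the detectable difference is then 1.294 SD/year, or 0.647 SD at 6 months, which round to the printed values. Even with that slip, 20 per group gives only 75%.

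**The case against.** The strongest reply is that the trial will hold more data than the calculation uses. Section 4 schedules blood at screening, the additional blood test, baseline and months 1, 3 and 6. Suppose all three pre-treatment values are placed at time 0, month 1 is added, and every pair correlates at 0.54. The slope model then gives 78% power at 1.3 SD/year with 20 per group (81% with a common baseline). For 0.63 SD it gives 81% with 23 per group and 90% with 30. This stands as a point about what the trial could achieve. It does not rescue the printed figure, because Section 7 powers three measurements and does not say that screening values enter the model. Those screening values were also used to select participants.

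A second reply is that 20 per group is not the planned number. That is fair: with all 30 per group retained, power for 0.63 SD is 72% under the stated model and 83.5% with a common baseline. But the plan itself expects 46 completers, and at 23 per group the figures are 61% and 73%.

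A third reply is that the plan leaves covariance structure, baseline handling and sidedness of the slope test unstated, so 57% also depends on a chosen model. That stands as a reason to ask for the formula. A one-sided test with a common baseline would reach about 80%, but the plan states neither.

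Finally, this is the second calculation in a pilot, and no endpoint, test or sample size depends on correcting it. That bears on urgency. It does not make the figure right.

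**Conclusion.** The concern holds. On its stated inputs, the slope analysis has about 57% power for 1.3 SD/year and not 80%; it detects 1.70 SD/year (0.85 SD at 6 months) with 80% power. The statement of adequate power for 0.63 SD fails under the stated model at 20, 23 and 30 per group (55%, 61% and 72%). At the 20 per group used in the calculation and the 23 expected completers, the chance of missing that effect is about 40–45%.

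These figures assume a two-sided 0.05 test, equal correlation of 0.54 between visits, separate group intercepts and the three visits named in Section 7. Models that use baseline adjustment or the extra blood draws do better, in some cases reaching 80%, but the plan does not specify them.

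**What to change.** In Section 7, replace the slope power statement with text such as:

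> With 20 per group the slope comparison (two-sided 0.05, equal correlation 0.54, visits at 0, 3 and 6 months) has 80% power for 1.70 SD/year, or 0.85 SD at 6 months. With the expected 23 completers per group it has 80% power for 1.59 SD/year, or 0.79 SD.

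Delete the claim of adequate power for 0.63 SD, or replace it with the actual figures (55% at 20 per group, 61% at 23). State the formula, the sidedness, the correlation structure and the visits used.

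If a detectable difference near 0.63–0.65 SD is wanted, name the analysis that would support it, such as a baseline-adjusted model or one using the additional blood draws, and show its calculation.

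The cost is wording only. Enrolment need not change, but the stated power becomes less favourable.
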